Simulations performed using an asciminib population PK model revealed that a dose of 40 mg BID maintains C_{troughs} above the clinical (0.07 to 61 ng/mL) threshold in ≥95% of chronic phase CML patients without T315I mutation having failed ≥ 2 TKI or intolerant to TKIs. The estimates from this clinical study were found to be similar to the threshold trough concentration required for 90% inhibition of pSTAT5 derived from a preclinical PK-PD KCL-22 mouse xenograft model (free IC₉₀: 30 to 121 ng/mL, after correction for protein binding) and *in vitro* gIC₅₀ assessed in the KCL-22 cell line (1 ng/mL = 2.1 nM after correction for protein binding).

Simulations performed using asciminib population PKPD model revealed that chronic phase CML patients having failed ≥ 2 TKI or intolerant to TKIs are likely to exhibit a 1 log₁₀ reduction of (%) BCR-ABL1 mRNA transcript levels from baseline of ~33% (CI_{95%}: 24-42%) at 6 months, and ~42% (CI_{95%}: 32-52%) at 12 months at a dose of 20 mg BID and ~41%

(CI95%: 31-51%) at 6 months, and ~53% (CI95%: 43-63%) at 12 months at a dose of 40 mg BID.

Additional preliminary exposure response analyses (i.e. exploring the relationship between PK and both safety and efficacy) support the selected dose.

Food effect

The effect of food on asciminib PK was characterized in a Phase I study [CABL001A2101] in healthy volunteers. Food was found to influence the pharmacokinetics of asciminib. When administered with a low-fat meal, the exposure (AUC) decreased by approximately 30%. The overall exposure decreased by approximately 65% when administered with a high-fat meal. Therefore, asciminib will be administered in a fasted state.

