6.1.1 Dosing regimen

Asciminib

Asciminib 20 or 40 mg strength tablets will be administered orally twice-daily (BID), without food. Asciminib tablets should be ingested as follows:

- Asciminib should be administered in the fasted state: avoid food for at least 2 hours before the dose is taken and for at least 1 hour after the dose is taken. Water is permitted during this period.
- Asciminib should be taken with approximately 8 ounces (240 mL) of water.
- Asciminib should be swallowed whole and not chewed or crushed.
- If vomiting occurs within the first hour after taking the drug, re-dosing is allowed before the next scheduled dose

- If the patient does not take asciminib within 6 hours after the approximate time of the usual dosing time, that dose should be skipped and treatment should continue with the next daily dose at the prescribed level

Bosutinib

Bosutinib 500 mg or 100 mg tablets will be administered orally once daily (QD) with food. If a dose is missed beyond 12 hours, the patient should skip the dose and take the usual dose on the following day.

Table 6-1 Dose and treatment schedule

Study treatments	Pharmaceutical form and route of administration	Dose	Frequency and/or Regimen	Fasting Condition
Asciminib	Tablet for oral use	20 mg ^a	Twice-daily	Fasting
Asciminib	Tablet for oral use	40 mg	Twice-daily	Fasting
Bosutinib	Tablet for oral use	100 mg ^b	Once-daily	Non-fasting
Bosutinib	Tablet for oral use	500 mg	Once-daily	Non-fasting

^a 20 mg tablets will be dispensed to patients in the instance of dose reduction.

^b 100 mg tablets will be dispensed to patients in the instance of dose modifications.

On days when serial blood samples are collected for asciminib PK analysis, patients will be instructed to bring their drug supply to the site, and take the dose in the clinic, under supervision of the site personnel. The exact time for dose administration and meal intake must be recorded in the electronic Case Report Form (eCRF).

All dosages prescribed and dispensed to the patient and all dose changes during the study must be recorded on the Dosage Administration Record eCRF.

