7.2.3 Pharmacokinetics

Blood samples for asciminib pharmacokinetics will be collected on all study subjects allocated to the asciminib treatment arm. Blood samples for full PK profiles will be collected from at least 20 patients. These patients will be identified sequentially at selected sites that are capable of serial PK sampling over 12 hours. Asciminib should be taken for at least 3 consecutive days without interruption or dose modification prior to full PK day.

Blood samples for asciminib pharmacokinetics will also be collected on patients switching from bosutinib to asciminib (see [Table 7-8](#)).

For the assessment of asciminib pharmacokinetics in plasma, serial blood samples will be collected following asciminib administration at several time-points (see [Table 7-1](#), [Table 7-2](#), [Table 7-8](#) and [Table 7-9](#) below for further details). Remaining plasma samples may be used for identification and/or measurement of metabolites of asciminib.

Refer to the [[CABL001A2301 Laboratory Manual](#)] for detailed instructions for the collection, handling, and shipment of PK samples.

Table 7-8 Pharmacokinetic blood collection log (Sparse PK-group-asciminib arm/ asciminib treatment switch patients)

Week / S-Week	Day	Scheduled Time Point	Dose Reference ID	PK Sample No	Blood Volume (mL)
1	1	2 h (± 10 min)	101	101	2
2	1	0 h (Pre-dose) ^a	102/2001 ^b	102	2
	1	2 h (± 10 min)	102	103	2
	1	3 h (± 15 min)	102	104	2
	1	4 h (± 15 min)	102	105	2
4	Any	0 h (Pre-dose) ^a	103/3001 ^b	106	2
12	Any	0 h (Pre-dose) ^a	104/4001 ^b	107	2
24	Any	0 h (Pre-dose) ^a	105/5001 ^b	108	2
96	Any	0 h (Pre-dose) ^a	106/6001 ^b	109	2
		Unscheduled		1001+	

^a Pre-dose PK sample should be taken immediately prior to the next administration of asciminib. PK samples on Week 2 Day 1 should be taken before and after the morning dose (i.e. 1st dose of the day). PK samples on other weeks may be taken immediately prior to the morning dose (i.e. 1st dose of the day) or the evening dose (i.e. 2nd dose of the day).

^b The first dose reference ID refers to the first dose administered after PK sampling and the second dose reference ID refers to the last dose administered prior to the PK sampling.

[figure not shown]

Table 7-9 Pharmacokinetic blood collection log (Full PK group-asciminib arm)

Week	Day	Scheduled Time Point	Dose Reference ID	PK Sample No	Blood Volume (mL)
1	1	2 h (± 10 min)	1	1	2
2	1	0 h (Pre-dose) ^a	2/201 ^b	2	2
	1	0.5 h (± 10 min)	2	3	2
	1	1 h (± 10 min)	2	4	2

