10.1.5 Pharmacokinetic analysis set

The **Pharmacokinetic analysis set (PAS)** includes all patients who provide at least one evaluable PK concentration. For a concentration to be evaluable, patients are required to:

- Take a dose of asciminib prior to sampling,
- Take the same dose of asciminib for at least 3 consecutive days without dose interruption or dose modification prior to sampling,
- For post-dose samples, do not vomit within 4 hours after the dosing of asciminib (this is the current dose); for pre-dose samples do not vomit within 4 hours after the dosing of asciminib prior to sampling (this is the previous dose),
- Have the pre-dose sample collected before the next dose administration.

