10.5.4 Secondary PK objectives

The PK objective is to characterize the PK of asciminib in CML population.

Using PAS, summary statistics (n, mean, SD, coefficient of variation (CV) for mean, geometric mean, CV for geometric mean, median, minimum and maximum) will be presented for plasma concentration at each scheduled time point. The geometric mean with mean (SD) and individual plasma concentration versus time profiles of asciminib will be displayed graphically.

Using Safety set, concentration data will be listed. Concentration values below the limit of quantification (BLQ) will be set to zero by the Bioanalyst and displayed in listings as zero with a flag. BLQ values will be handled as zero in any calculations of summary statistics, but handled as missing for the calculation of the geometric means and CVs.

Pharmacokinetic parameters will be determined by non-compartmental method(s) using the pharmacokinetic profile of asciminib in patients with full PK sampling. PK parameters listed in [Table 10-1](#) will be derived and reported, when feasible.

Population PK modeling may be performed and the results may be reported in a separate population PK report. Data from this study may be combined with data from other studies for this analysis.

Table 10-1 Non compartmental pharmacokinetic parameters in full PK group

AUC0-12h	The area under the plasma concentration-time curve from time zero to 12 h (mass x time x volume-1) ^a
Cmax	The maximum (peak) observed plasma drug concentration after dose administration (mass x volume-1)
Tmax	The time to reach maximum (peak) plasma drug concentration after dose administration (time)
CL/F	The total body clearance of drug from the plasma after oral administration (volume x time-1)

[figure not shown]

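### The trough summaries set no limit on time since the previous asciminib dose and no split by actual dose, so compliant samples can be mistimed and two dose levels mixed

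*Combined protocol and SAP*

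**What the plan says.** Table 3-1 lists trough plasma concentrations as an endpoint for the secondary PK objective. Section 10.1.5 decides which concentrations are evaluable. Besides a prior dose and no vomiting within 4 h of the relevant dose, it has two conditions that matter here:

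- Dosing history: "Take the same dose of asciminib for at least 3 consecutive days without dose interruption or dose modification prior to sampling". No dose level is named.
- Timing of a pre-dose sample: "Have the pre-dose sample collected before the next dose administration".

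The collection instruction is footnote a of Tables 7-8 and 7-9: "Pre-dose PK sample should be taken immediately prior to the next administration of asciminib". The same footnote adds, for visits other than Week 2: "PK samples on other weeks may be taken immediately prior to the morning dose (i.e. 1st dose of the day) or the evening dose". Post-dose samples in these tables have windows from ±10 to ±60 min. The 0 h pre-dose samples at Weeks 2, 4, 12, 24 and 96 have none. One pre-dose sample does: in the full PK group, the second pre-dose sample on Week 2 Day 1 is set at 12 h ± 60 min.

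Section 6.1.1 governs late doses: "If the patient does not take asciminib within 6 hours after the approximate time of the usual dosing time", the dose is skipped; a delay of up to 6 h is therefore tolerated. Section 10.5.4 says that the summary statistics "will be presented for plasma concentration at each scheduled time point"; it mentions no split by actual dose.

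**The concern.** A trough on a twice-daily schedule is meant to describe exposure about 12 h after a dose. The plan ties the sample to the dose that follows it, while the value depends on the time since the dose before it. When doses shift within the tolerated limits, a correctly collected and evaluable sample need not be a 12 h value, and nothing in Section 10.1.5 identifies it.

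Separately, a patient reduced to 20 mg BID becomes evaluable after three stable days and enters the same time-point summary as patients on 40 mg BID.

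At stake is what the trough tables can be read as. Section 1.2.1.2 supports 40 mg BID partly by simulated troughs that stay above a threshold in at least 95% of patients. The trough tables of this trial are the natural place to check that, and mixed elapsed times and dose levels blur the check.

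**Working it through.** The plan gives no figure of its own on this point, so there is none to reproduce. The size follows from these inputs:

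- Dosing interval: 12 h nominal (BID).
- Tolerated delay: 6 h (Section 6.1.1).
- Half-life: 7 to 15 h, the median accumulation half-life (Section 1.2.1.2, Pharmacokinetics).
- Exposure approximately dose proportional (same section).
- Dose levels: 40 mg and 20 mg BID (Table 6-3).

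**Permitted elapsed time.** Previous dose 6 h late, next dose on time: 12 − 6 = 6 h. Previous dose on time, next dose 6 h late: 12 + 6 = 18 h. In both cases the sample can be taken right before the next dose, as footnote a asks.

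**Effect on the reading.** Assume mono-exponential decline: C(t)/C(12) = 2^((12 − t)/half-life).

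| Hours after previous dose | Half-life 7 h | Half-life 15 h |
|---|---|---|
| 6 | 2^(6/7) = 1.81 | 2^(6/15) = 1.32 |
| 10 | 1.22 | 1.10 |
| 11 | 1.10 | 1.05 |
| 13 | 0.91 | 0.95 |
| 14 | 0.82 | 0.91 |
| 18 | 2^(−6/7) = 0.55 | 2^(−6/15) = 0.76 |

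The 6 h row reads the regular steady-state curve at an earlier time. If only one dose is late, it is added to a lower residual. Take superposition with immediate absorption (a further assumption) and write a = 2^(−12/half-life). The ratio is then 2^(6/half-life) × (1 − a) + a:

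- Half-life 7 h: a = 0.305, so 1.811 × 0.695 + 0.305 = 1.56.
- Half-life 15 h: a = 0.574, so 1.320 × 0.426 + 0.574 = 1.14.

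So 1.81 is an outer limit on the high side. The 18 h row is unaffected, because there the previous doses were on time.

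**Effect of mixing doses.** If a share s of samples is at half the dose, the arithmetic mean is multiplied by 1 − s/2 and the geometric mean by 0.5^s. The documents give no s; 10-30% is assumed.

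| s | Arithmetic mean | Geometric mean |
|---|---|---|
| 10% | 0.95 (5% lower) | 0.933 (about 7% lower) |
| 20% | 0.90 (10% lower) | 0.871 (about 13% lower) |
| 30% | 0.85 (15% lower) | 0.812 (about 19% lower) |

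**The case against.** The strongest reply is that collection is already controlled. Footnote a calls for sampling immediately before the next dose, one pre-dose sample has a numeric window, and three days of uninterrupted dosing are required. The 6 h and 18 h cases need a dose delayed by the full allowance right next to the sample. This stands against any reading that the plan accepts a sample at an arbitrary time since the last dose. It does not close the gap: the footnote says nothing about the previous dose, and Section 10.1.5 has no matching exclusion.

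Four stronger inferences are tempting and are not supported:

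- **A 20 mg sample is not a trough.** After three stable days it is one. Only its pooling with 40 mg values is at issue.
- **The plan admits fed doses by design.** Section 6.1.1 requires fasting at every dose, so a fed dose is a deviation. Section 1.2.1.2 does report "The overall exposure decreased by approximately 65% when administered with a high-fat meal", and about 30% for a low-fat meal, but these are overall-exposure figures in healthy volunteers, not effects on trough.
- **Exposure-response will use mistimed values.** Section 10.6.2 says such analysis may be done, offers trough only as an example, and leaves details to the SAP. A range of doses is not in itself an error there.
- **Pooled troughs will drift down to Week 96.** Section 6.3.1 allows one re-escalation to 40 mg BID and, cytopenias apart, has patients stop if toxicity recurs at the lower dose. The direction over time cannot be predicted.

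**Conclusion.** The point holds in a limited form. The evaluability rule has no limit on time since the previous dose, and the summaries have no stated split by dose. Following the text as written, the trough tables can therefore contain values from about 6 to 18 h after dosing and from two dose levels.

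The timing effect ranges from 0.55 to 1.81 times the 12 h value. It rests on mono-exponential decline and on using the accumulation half-life as the decline rate. How often such values occur is unknown. The 5-15% dose-mix effect rests entirely on the assumed share at 20 mg. If the SAP already specifies a window or a by-dose table, the point falls to that extent.

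The consequence is confined to a descriptive secondary PK endpoint and possibly to optional exposure-response work. No hypothesis test and no primary or key secondary efficacy result depends on it. It is a cheap improvement to the analysis text.

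**What to change.** 1. In Section 10.1.5, include a pre-dose concentration in the trough summaries only if recorded times place it within a pre-specified window around 12 h after the previous dose. An example is 12 h ± 2 h, which under the same assumption keeps readings within 0.82 to 1.22 times the 12 h value. Table 7-9's 12 h ± 60 min is a precedent for a narrower one (0.91 to 1.10).
2. In Section 10.5.4, summarise concentrations by actual dose (40 and 20 mg BID) at each scheduled time point.
3. Keep out-of-window values in the listings, and in any population PK model at their actual times.
4. Where the meal record covers the previous dose, flag samples that follow a non-fasted dose and repeat the summary without them. This should be a flag with a sensitivity summary, not a general exclusion: before a morning sample the previous dose was taken the evening before, and the documents do not show that meals around it are recorded.

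The cost is mainly analysis wording. Tables 7-8 and 7-9 already carry a reference ID for the previous dose, and dose changes are recorded in the eCRF. Section 6.1.1 states that "The exact time for dose administration and meal intake must be recorded in the electronic Case Report Form", but for serial sampling days, so the sponsor should confirm that the clock time of the previous dose is captured at the single-trough visits. The downside is somewhat fewer values in the trough tables.

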10.1.6 Other analysis set

For duration of MMR and time to MMR, the MMR Responder Set that will be used is a subset of FAS and includes patients who achieve MMR at any time.

For CCyR rates at and by scheduled time points, the CCyR Analysis Set that will be used is a subset of FAS and includes patients who are not in CCyR at baseline.

For duration of CCyR and time to CCyR, the Cytogenetic Responder Set that will be used is a subset of FAS and includes patients who do not have CCyR at baseline and achieve CCyR at any time on study treatment.

Patients who will receive at least one dose of asciminib after bosutinib failure will form the Switch Analysis Set which will be used for safety and exploratory efficacy endpoints defined on these patients.

10.2 Patient demographics/other baseline characteristics

Demographic and other baseline data including disease characteristics will be listed and summarized descriptively by treatment group for the FAS or the Safety Set.

Categorical data will be presented as frequencies and percentages. For continuous data, mean, standard deviation, median, minimum, and maximum will be presented.

[figure not shown]
Relevant medical histories and current medical conditions at baseline will be summarized separately by system organ class and preferred term, by treatment group.

10.3 Treatments (study treatment, concomitant therapies, compliance)

The Safety set will be used for the analyses below.

Categorical data will be summarized as frequencies and percentages. For continuous data, mean, standard deviation, median, 25th and 75th percentiles, minimum, and maximum will be presented.

The duration of exposure in days to asciminib and bosutinib, as well as the dose intensity (computed as the ratio of actual cumulative dose received and actual duration of exposure) and

the relative dose intensity (computed as the ratio of dose intensity and planned dose intensity) will be summarized by means of descriptive statistics.

The number of patients with dose adjustments (reductions, interruption, or permanent discontinuation) and the reasons will be summarized by treatment group and all dosing data will be listed.

Concomitant medications and significant non-drug therapies prior to and after the start of the study treatment will be listed and summarized according to the Anatomical Therapeutic Chemical (ATC) classification system, by treatment group.

10.4 Primary objective

The primary objective of the study is to evaluate the efficacy of asciminib at the recommended dose in CML patients in chronic phase, previously treated with 2 or more tyrosine kinase inhibitors and to compare this efficacy profile in this population with that achieved by patients receiving bosutinib.

10.4.1 Variable

The primary efficacy variable of the study is the Major Molecular Response (MMR) rate at 24 weeks. A patient will be counted as having achieved MMR at 24 weeks if he meets the MMR criteria (BCR-ABL1 ratio $\leq 0.1\%$) at 24 weeks.

10.4.2 Statistical hypothesis, model, and method of analysis

The MMR rate at 24 weeks will be calculated based on the FAS and according to the Intention-To-Treat (ITT) principle. MMR rate and its 95% confidence interval based on the Pearson-Clopper method will be presented by treatment group. The confidence interval for the difference in MMR rate between treatment groups will be provided using the Wald method.

The null hypothesis is that there is no difference between the treatment groups with respect to MMR rate at 24 weeks. The Cochran-Mantel-Haenszel chi-square test, stratified by the randomization stratification factor, i.e. major cytogenetic response status (PCyR or CCyR vs. others) at screening, will be used to compare MMR rate between the two treatment groups, at the two-sided 5% level of significance. The Mantel-Haenszel estimate of the common risk difference and the corresponding 95% confidence interval will also be provided.

10.4.3 Handling of missing values/censoring/discontinuations

Only patients with MMR at 24 week visit are considered responders. In other words, any patient who achieves MMR before 24 weeks, but is no longer in MMR at 24 weeks, will be considered as a non-responder in this primary analysis. Patients discontinuing the randomized treatment (having performed an EOT visit) prior to 24 weeks due to any reason will be considered as non-responders. One exception to the rule above is if the 24-week PCR evaluation is missing, but both a PCR evaluation at 16 weeks and a PCR evaluation at 36 weeks indicate MMR, the 24-week assessment is imputed as a 'Response'. If PCR evaluations are performed at unscheduled visits closer to the Week 24 visit (before or after), these will be taken into account for the imputation.

10.4.4 Supportive and Sensitivity analyses

The analysis of the primary endpoint will also be repeated on the PPS if the PPS is different from the FAS.

Subgroup analyses and a logistic regression analysis will be employed. Refer to the exploratory objectives [Section 10.6.1](#) for further details.

10.5 Secondary objectives

The secondary objectives in this study are as follows:

- To compare additional parameters of the efficacy of asciminib versus bosutinib, defined as:

Key secondary endpoints

[figure not shown]
- MMR rate at 96 weeks

Other efficacy endpoints

- Cytogenetic response (Complete, Partial, Major, Minor, Minimal, no response) rate at all scheduled data collection time points including, 24, 48 and 96 weeks.
- Cytogenetic response (Complete, Partial, Major, Minor, Minimal, no response) rate by all scheduled data collection time points including, 24, 48 and 96 weeks.
- MMR rate at all scheduled data collection time points (except 24 and 96 weeks which are already covered by primary and key secondary endpoints)
- MMR rate by all scheduled data collection time points including 24, 48 and 96 weeks.
- Time to MMR
- Duration of MMR
- Time to CCyR
- Duration of CCyR
- Time to treatment failure
- Progression free survival
- Overall survival
- To compare the safety and tolerability profile of asciminib versus bosutinib
- To characterize the PK of asciminib in the CML-CP population

10.5.1 Key secondary objective(s)

The key secondary endpoint to be evaluated is MMR rate at 96 weeks, which is defined as the proportion of patients with MMR at 96 weeks and derived in a similar fashion to MMR rate at 24 weeks.

10.5.1.1 Analysis for key secondary objectives

The null hypothesis is that there is no difference between the treatment groups with respect to MMR rate at 96 weeks. Formal statistical testing of the key secondary endpoint will be performed with $\alpha = 0.05$ (two-sided) only if the primary endpoint (i.e. MMR rate at 24 weeks) is significant by means of a gatekeeping procedure to control the overall alpha level. Otherwise, no statistical testing will be performed, and any analysis will be considered exploratory.

MMR rate at 96 weeks will be evaluated in a similar fashion to the primary analysis of MMR rate at 24 weeks. The rate and the associated 95% confidence interval based on the Pearson-Clopper method will be presented by treatment group. Confidence interval for the difference between treatment groups will be provided using the Wald method.

Statistical testing will be performed via CMH chi-square test stratified by the randomization strata. The Mantel-Haenszel estimate of the common risk difference and the corresponding 95% confidence interval will also be provided.

If the PCR evaluation at 96 weeks is missing, but a PCR evaluation both at 84 weeks and 108 weeks indicate MMR, the 96 week assessment is imputed as a “response”, assuming that MMR is maintained between 84 and 108 weeks. If PCR evaluations are performed at unscheduled visits closer to the Week 96 visit (before or after), these will be taken into account for the imputation.

